## **5 STUDY METHODOLOGY**

### **5.1 Efficacy Outcomes**

- The **primary endpoint**:  
Proportion of subjects with any of the following COVID-19 symptoms: fever, cough, shortness of breath or anosmia, at day 3, 7, 10 and 14.
- The **secondary endpoints**:
  - 1- Mean number of COVID-19 symptoms (range 0 – 13) at day 3, 7, 10 and 14.
  - 2- Duration of COVID-19 symptoms, defined as the number of days between first symptoms and complete disappearance of any symptom.
  - 3- For each COVID-19 symptom listed in the appendix, proportion of subjects with the symptom at day 3, 7, 10 and 14.

Duration of symptoms will be determined as follows:

- If randomization and study product reception by participant occur the same day, first day of symptoms will be defined as the day of randomization;
- If randomization and study product reception by participant occur on different days, first day of symptoms will be defined as the day of study product reception.

- The **exploratory endpoints**:
  - 1- For each COVID-19 symptom listed in the appendix, proportion of subjects with the symptom on a daily basis based on patients' diary.
  - 2- Composite of COVID-19-related hospitalization, mechanic ventilation or death in the 14 days following randomization.

## 5.2 Safety Monitoring

Drug safety will be assessed by an evaluation of types, frequencies, severities and duration of any reported AEs.

### 5.2.1 Adverse Event Reporting

Information regarding AEs will be collected at day 3, 7, 10 and 14 after randomization. Any AEs prior to randomization will be recorded in the medical history and kept in the patients' chart.

All SAEs will be recorded on the appropriate eCRF section. Information collected will include the onset, duration, severity, relationship to study drug, and the management as outlined in Appendix C.

#### 5.2.1.1 Serious Adverse Events

Serious Adverse Events (SAE) are those that meet any of the following International Council for Harmonisation (ICH) criteria:

- Is fatal or immediately life-threatening;

- Results in persistent or significant disability/incapacity;
- Requires or prolongs inpatient hospitalization;
- Is a congenital anomaly/birth defect in the offspring of the patient;
- Is a cancer;
- Is an overdose (intentional or accidental);
- Is judged to be medically important.

Medically important events may not be immediately life-threatening or result in death or hospitalization but may jeopardize the patient or may require intervention to prevent one of the outcomes listed in the definition above. Serious Adverse Events are to be reported if they are known to occur within 14 days after randomization.

Medical and scientific judgment should be exercised in deciding whether other AEs meet these criteria and are immediately reportable to the sponsor or designee.

In the event of a serious or life-threatening adverse event, or in the event of death, immediately report the event on the appropriate SAE form in the eCRF.

**FOR ANY SAFETY QUESTIONS OR CONCERNS, PLEASE CONTACT:  
MHICC Medical Monitor**

**Email: [Hesperco\\[contact]](mailto:[contact])**

If any SAE occurs, the study treatment may be interrupted or discontinued at the Investigator's discretion. If an acute medical emergency occurs, the investigator may break the randomization code at any time if this is required for proper treatment of the patient and inform the person listed above by email.

The MHICC Medical Monitor or his designated representative is responsible to report any Suspected Unexpected Serious Adverse Reaction (SUSAR) to the regulatory authorities and to notify Ingenew Pharma at time of submission. Reports to the Health Authorities must be made within 7 calendar days, (for death and life-threatening events) and within 15 calendar days (for other serious events) after being informed of an SAE by the investigator.

#### **5.2.1.2 Adverse Event Follow-Up**

Record all reportable serious and non-serious AEs on the appropriate eCRF including the onset, duration, severity, relationship to the study drug, and ultimate management. All AEs reported during the treatment phase should be recorded and followed until the AE has subsided, or stabilized or until the end of the study, whichever occurs first. The study will be stopped at any time if new knowledge is gained and the risk-benefit ratio is no longer favorable for the participating patients and Ingenew Pharma will then be informed immediately but no later than 3 business days if such decision is made

### **5.3 Withdrawal of Patients from the Study**

Patients have the right to withdraw from the study at any time during the course of the study. However, every effort should be made, within the bounds of safety, patient choice and the provisions of informed consent, to have each patient complete the study up to and including the last protocol-specified phone call at Day 14. If the study medication jeopardizes the patient's health or if the patient wishes to discontinue for any reason, study medication can be discontinued but the patient should be encouraged to remain in the study for the follow-up phone calls up to Day 14. Patients who are not compliant during the active treatment period should be counseled on the importance of complying with study requirements and be allowed to remain in the study. No patient who has withdrawn his/her consent from the study during the active treatment period should be replaced.

In the case of an adverse event or safety concern, the study medication may be withheld temporarily, or the dose reduced, as per investigator judgment. Investigators should discuss the patient condition with the MHICC medical monitor in order to determine the appropriate dose reduction algorithm or study medication discontinuation plan.

Patients withdrawn at any time from the study during the active treatment period should complete all last protocol-specified phone call assessments at Day 14 (the reason for withdrawal from the study, the date of the last videovisit/phone call and the date of the last dose of double-blind medication will be clearly documented in the eCRF).

#### **5.4 Study Completion**

The study will end when the last randomized patient will have completed his (or her) 14-day follow-up phone contact or videovisit. Completion of the study by a patient should be clearly indicated in the eCRF, along with the date of the last phone call and the date of the last dose of double-blind medication.

### **6 STUDY MEDICATION**

Ingenew Pharma will provide both hesperidin and placebo in bulk to MHI pharmacists who will prepare the bottles of 32 capsules of 500 mg each. At the time of randomization, the randomization number will be recorded on the appropriate eCRF section. Blinded medication will be provided as 500 mg hesperidin capsules or matching placebo capsules. A detailed set of dispensing instructions will be provided by the MHICC.

#### **6.1 Medication Dispensing**

Study medication may be dispensed by the designated pharmacist according to a detailed set of dispensing instructions. Study medication will be shipped directly to the patient's home.

#### **6.2 Dosage Regimen**

At randomization, patients will be dispensed hesperidin capsule or matching placebo. Patients will be instructed to take two capsules once daily at bedtime according to the detailed set of dispensing instructions outlined on the label.

Orally, hesperidin is generally well tolerated. Headache, asthenia, muscle cramps, and gastrointestinal side effects such as abdominal pain, dyspepsia, nausea, and diarrhea may occur in some patients. There may be unknown risks with taking the investigational product.

## **7 DATA COLLECTION**

Electronic Case Report Forms (eCRF) for all patients will be supplied by MHICC. These are to be completed as instructed.

## **8 DATA ANALYSIS AND STATISTICAL CONSIDERATIONS**

### **8.1 Statistical Power and Sample Size Considerations**

Sample size is based on the proportion of subjects with any of the following COVID-19 symptoms: fever, cough, shortness of breath or anosmia at day 7 since this time point will be the primary focus. Using a two-sided 0.05 significance level, sample sizes of 91 in both groups (182 total) will achieve 80% power to detect an absolute between groups difference of 20% in the proportion of subjects with the above COVID-19 symptoms at day 7. This is assuming that the proportions of patients with the above COVID-19 symptoms at day 7 will be 50% in the placebo group and 30% in the active treatment group. Factoring in a 15% drop out rate, a total of 216 patients will be randomized in the study (108 per group).

### **8.2 Analysis population**

#### **8.2.1 Intent to Treat (ITT) population**

All patients randomized will be included in the ITT population. Patients will be assigned to treatment groups as randomized for analysis purposes.

#### **8.2.2 Safety population**

All patients who received at least one dose of study medication will be included in the safety analysis population. Patients will be assigned according to the true treatment received for analysis purposes.

### **8.3 Data analysis**

#### **8.3.1 Analysis of efficacy outcomes**

Efficacy analysis will be based on the intent-to-treat principle. The primary analysis will compare the proportions of subjects with fever, cough, shortness of breath or anosmia between the two treatment groups using a generalized linear mixed model with terms for treatment group (placebo, hesperidin), time (3, 7, 10 and 14 days) and treatment group x time interaction. The primary analysis will be the comparison between treatment groups at day 7, although treatment groups will also be compared at the other time points. Mean number of COVID-19 symptoms will be compared between treatment groups using a Student t-test or a Wilcoxon rank-sum test according to distribution. If more appropriate, a Poisson regression model will be used. Duration of COVID-19 symptoms will be compared between treatment groups using a log rank test and Kaplan-Meier curves will be presented. Subjects who will still have COVID-19 symptoms at the end of the study will be censored at the day of their last phone contact or videovisit. The analysis of individual COVID-19 symptoms over time will be similar to the analysis of the primary endpoint and will use generalized linear mixed models. Composite of COVID-19-related hospitalization, mechanic ventilation or death will be compared between treatment groups using a chi-square test. All statistical tests will be two-sided and conducted at the 0.05 significance level. Statistical analysis will be done using SAS version 9.4 or higher.

Full details of the statistical analysis will be described in a statistical analysis plan that will be finalized and approved prior to database lock.

### **8.3.2 Analysis of safety outcomes**

Safety of hesperidin will be evaluated by presenting descriptive statistics on adverse events and serious adverse events broken down by group. This will be done for the population of patients who received at least one dose of study medication (safety population).

### **8.3.3 Interim analysis**

A fully independent 3-member Data and Safety Monitoring Board (DSMB) will be established and will review unblinded safety data as detailed in the DSMB charter after randomization of 50 subjects and after randomization of 100 subjects. If necessary, an additional meeting will take place after randomization of 150 subjects. The DSMB charter will pre-specify the rules for early study termination, approved by all board members.

## **9 STUDY COORDINATION**

The MHICC will be responsible for processing and quality control of the data. Project management will be carried out as described in the MHICC standard operating procedures (SOPs) for clinical studies. The handling of data, including data quality control, will comply with all applicable regulatory guidelines, MHICC SOPs and the study Data Management Plan.

Appendix A      **Detailed Study Safety Parameters**

**1. Medical/Surgical History**

The following elements of medical/surgical history will be recorded at the Screening Visit:

- age
- ethnic origin
- sex
- smoking history
- history of diabetes
- history of hypertension
- history of dyslipidemia
- prior MI
- prior PCI
- prior CABG
- prior stroke
- prior heart failure
- prior obstructive pulmonary disease
- prior other respiratory disease

**2. Physical Appearance**

1. weight
2. height
3. waist circumference

## Appendix B      **Administrative Procedures for the Reporting of Adverse Events**

The following administrative procedures for reporting AEs are to be followed during the conduct of this clinical trial.

### **1    ADVERSE EVENTS DURING THE TRIAL**

Each patient will be observed and queried in a non-specific manner by the investigator or study coordinator at each visit for any new or continuing AE since the previous visit. Any AEs prior to the first dose of study medication will be recorded in the medical history and kept in the patients' chart. All SAEs will be recorded in the appropriate eCRF section. Information collected will include the onset, duration, severity, relationship to study drug, and the management. SAEs are to be reported if they are known to occur within 21 days after randomization.

The investigator will review concomitant medications being taken by the patient.

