#### **Definitions**

##### **1.1 Pre-existing condition**

A pre-existing condition is one that is present prior to randomization. A worsening of a pre-existing condition after taking the first dose of investigational product should be reported as an AE.

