##### **1.4 Serious Adverse Event (SAE)**

Serious Adverse Events (SAE) are those that meet any of the following International Council for Harmonisation (ICH) criteria:

- Is fatal or immediately life-threatening (NOTE: the term "Life-Threatening" refers to an event in which the patient was at immediate risk of death at the time of the event; it does not refer to an event which could hypothetically have caused death had it been more severe);
- Results in persistent or significant disability/incapacity;
- Requires or prolongs patient hospitalization;
- Is a congenital anomaly/birth defect in the offspring of the patient;
- Is a cancer;
- Is an overdose (intentional or accidental);
- Is judged to be medically important.

Medically important events may not be immediately life-threatening, result in death or hospitalization, but may jeopardize the patient or may require intervention to prevent one of the outcomes listed in the definition above. Serious adverse events are to be reported if they are known to occur within 21 days after randomization.

Medical and scientific judgment should be exercised in deciding whether other AEs meet these criteria and are immediately reportable to the sponsor or its designee.

Hospitalization is defined as a patient admission to a hospital for medical treatment or observation; a visit to the emergency room for an outpatient consultation is not considered a hospitalization. Moreover, hospitalization for therapy of the target disease(s) of the study if the protocol explicitly anticipated and defined the symptoms or episodes is not considered SAEs.

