#### **3.3 Hospitalization or Surgery/Procedure**

Any AE that results in hospitalization (admitted and not just an emergency room visit) should be reported as an SAE. Any condition/diagnosis responsible for surgery/procedure should be reported as an AE if it meets the criteria for an AE. A medical procedure is not considered and should not be reported as an AE. The surgery/procedure itself will be reported as a Clinical Outcome of the underlying event. Events that prolong any hospitalization are reported as SAEs.

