#### 4.3 Tertiary (or Exploratory) Efficacy Endpoints

- For each of the 13 COVID-19 symptoms listed in the appendix, proportion of subjects with the symptom on a daily basis based on patient's diary. Presence of these symptoms (Yes/No) will be identified using the Covid-19 Symptoms Form of the eCRF (variables COUGH, FEVER [considered a symptom if greater than 38°], FEVERISH, STHROAT, ..., ANOS) at DAY 1 to DAY 14.
- Composite of COVID-19-related hospitalization, mechanic ventilation or death in the 14 days following randomization. These events will be identified using the Adverse Events Form of the CRF:
  - ✓ COVID-19 related hospitalization: AECOVID=YES and AESER=YES and AESHOSP=YES; date of hospitalization = ADMDAT
  - ✓ COVID-19 related mechanic ventilation: AECOVID=YES and AEVENT=YES; date of mechanic ventilation = AEVSDTA
  - ✓ COVID-19 death: AECOVID=YES and AEOUT=Fatal; date of death = AEENDAT1

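### Appendix B starts adverse-event recording at the first dose, protocol 5.2.1 and SAP 5.1 at randomization, so a COVID-19 admission in between could be misfiled and missed by the exploratory 14-day composite

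*Protocol*

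**What the plan says.** Two cut-offs are in force for the same decision, namely whether an event is an adverse event or medical history.

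- **First dose.** Appendix B section 1: "Any AEs prior to the first dose of study medication will be recorded in the medical history". Appendix B 1.1 follows the same line: "A worsening of a pre-existing condition after taking the first dose of investigational product should be reported as an AE".
- **Randomization.** Protocol 5.2.1: "Any AEs prior to randomization will be recorded in the medical history". SAP 5.1 repeats this wording. Within Appendix B itself, section 1.7 also takes randomization as the baseline for a treatment-emergent sign or symptom.

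The composite of COVID-19-related hospitalization, mechanical ventilation or death covers the 14 days after randomization. SAP 4.3 and 6.4.3 attach no dosing condition to it. SAP 4.3 names one data source: "These events will be identified using the Adverse Events Form of the CRF". The hospitalization component also requires AESER=YES, that is, the event must be marked serious.

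Appendix B also has rules that point towards capture. Section 1 says "All SAEs will be recorded in the appropriate eCRF section" and "SAEs are to be reported if they are known to occur within 21 days after randomization". Section 3.3 says "Any AE that results in hospitalization (admitted and not just an emergency room visit) should be reported as an SAE". Section 4.2 requires study endpoints to be entered in the eCRF within five days of staff learning of them.

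**The concern.** Drug is shipped to the patient's home (protocol 6.1) and taken at bedtime (6.2). Section 5.1 provides for the product arriving on a later day than randomization. A randomized patient can therefore be untreated for a time while the composite's 14-day window is already running.

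Suppose such a patient worsens and is admitted before the first dose. Under 5.2.1 and SAP 5.1 the admission is an adverse event. Under the first-dose sentence of Appendix B it is medical history, kept in the chart. COVID-19 is present at entry in every patient, so its worsening also falls under Appendix B 1.1, which asks for a report only after the first dose. If staff follow those two sentences, nothing is entered on the Adverse Events Form, and the SAP's derivation counts the patient as event-free. What is at stake is a complete count for an exploratory endpoint that may have few events.

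**Working it through.** **1. The plan's own figure.** The documents give no number for this point. The only related figure is the sample size, which does not depend on it. With unpooled variance, n per group = (1.96 + 0.8416)² × (0.5×0.5 + 0.3×0.7) / 0.20² = 90.3, rounded up to 91. Allowing for dropout, 91 / 0.85 = 107.1, rounded up to 108, or 216 in total. The stated size reproduces and is not affected.

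**2. Following one admission through the rules.** Take a COVID-19 admission after randomization and before the first dose.

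- *Appendix B 1, first-dose sentence:* medical history. It covers any AE and makes no exception for serious ones.
- *Appendix B 1.1:* worsening of a pre-existing condition is not yet reportable.
- *Appendix B 1, SAE sentences:* to the eCRF, on a clock that starts at randomization.
- *Appendix B 3.3:* an SAE, provided it is first an AE. Appendix B 1.2 defines an AE by its association in time with use of the product, which leaves an undosed patient unclear.
- *Appendix B 1.4:* an exception to SAE status. Hospitalization for "therapy of the target disease(s) of the study if the protocol explicitly anticipated and defined the symptoms or episodes is not considered SAEs". COVID-19 hospitalization is a named endpoint, so staff could apply this.
- *Appendix B 4.2:* study endpoints go in the eCRF, with no dosing condition. The form is not named.
- *SAP 4.3:* the admission counts only if it is on the Adverse Events Form with AECOVID, AESER and AESHOSP all YES.

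Read together, the rules favour capture, but two sentences send the same admission elsewhere. The exception in 1.4 can also leave AESER unset for an admission that does reach the form, and it applies after the first dose too.

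**3. Upper limit on the events exposed.** The gap length and the 14-day risk are both assumptions. With a constant hazard, the share of the window in the gap is gap/14: 1 day 7.1%, 2 days 14.3%, 3 days 21.4%. Events in the gap = 216 × risk × gap/14.

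| Assumed 14-day risk | Total events | 1-day gap | 2-day gap | 3-day gap |
|---|---|---|---|---|
| 2% | 4.3 | 0.31 | 0.62 | 0.93 |
| 5% | 10.8 | 0.77 | 1.54 | 2.31 |
| 10% | 21.6 | 1.54 | 3.09 | 4.63 |

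These are all the events that would fall in the gap, not the number that would be misfiled.

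**The case against.** A reader might infer that Appendix B removes pre-dose admissions from the composite. The documents do not support that. Right after the first-dose sentence, Appendix B sends all SAEs to the eCRF, with a reporting window counted from randomization. Section 3.3 makes an adverse event that leads to admission an SAE. Section 4.2 gives endpoints their own route, and the visit table records potential endpoints from the first contact after randomization. The first-dose sentence is most naturally read as covering non-serious events.

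The SAP also appears to expect pre-dose events in the data. It lists all adverse events but summarizes only treatment-emergent ones. It assigns some partly dated composite events to the day of randomization, and it states that it supersedes the protocol where they differ. The Adverse Events Form carries COVID-19 and ventilation fields, so the endpoint route may well lead to that form. In addition, SAP 3.1 limits the ITT population to patients to whom drug was delivered, so a patient admitted before a delivery that never happens is outside the efficacy set rather than counted as event-free.

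Most of this stands, and it makes loss the exception. It does not remove the conflict. The first-dose sentence has no SAE exception, 1.1 agrees with it, and 4.2 does not name the form that the SAP reads. The SAP's precedence governs the analysis more clearly than what staff enter at the time of the event.

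A reader might also infer bias in the treatment comparison. Events before the first dose cannot be drug effects, and with blinded 1:1 allocation their loss should balance between the arms in expectation.

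**Conclusion.** The contradiction in cut-off is certain. Its consequence is conditional: a COVID-19 admission between randomization and first dose is lost from the composite only if staff apply the first-dose sentence, or the pre-existing-condition rule, to a serious event despite the rules that point towards capture. The harm is then under-counting in an exploratory endpoint.

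The range of 0.3 to 4.6 events rests on an assumed 2-10% risk, a 1-3 day gap and a constant hazard, none of which the documents supply. It is the most that could be exposed and should not be read as an expected loss. Eligibility excludes patients about to be hospitalized, which makes a constant hazard from day 0 doubtful.

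The primary day-7 analysis does not use these events. The treatment-emergent safety tables follow the first dose under SAP 5.1 and do not change. The correction is worth making because it is specific and nearly free.

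**What to change.** 1. Reconcile Appendix B 1 and 1.1 with protocol 5.2.1 and SAP 5.1, so that adverse-event recording, including worsening of a pre-existing condition, starts at randomization in every place.
2. Add one sentence to Appendix B: every COVID-19-related hospitalization, mechanical ventilation or death from randomization to day 14 is entered on the Adverse Events Form, whatever the dosing status.
3. Reconcile the target-disease exclusion in Appendix B 1.4 with the AESER=YES condition in SAP 4.3. Either state that the exclusion does not apply to COVID-19 admissions in this trial, or remove AESER from the derivation if the form allows AESHOSP to be completed without it. Without this step, an admission on the form could still fail the SAP's rule.

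The cost is administrative wording in the protocol, one line in the SAP, a note to the staff who enter data and possibly a few more forms. Sample size and primary analysis stay as they are. If recruitment has ended, the practical equivalent is a chart check before database lock, limited to patients whose first dose came after the day of randomization or who were never dosed.
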